4 STUDY DESIGN

- CO-OP Chicago is a two-arm cluster randomized controlled trial with repeated measurements. The comparison arm receives usual care. (After completion of the trial, the usual care arm will be offered limited CHW intervention.) The nature of the intervention allows for a single blind design in which data collection will be performed by research assistants.
- The trial targets healthy, low income, predominantly minority children under the age of 3 years old, and their families in Cook County, Illinois.
- This is a multi-center trial with two arms and 20 sites (clusters).
- We will recruit between 18-23 families from each site for a total sample size of 420. Sites are in two strata: medical clinic and WIC. These are combined for the primary analysis but will be compared to each other in the exploratory analysis.
- Study enrollment is scheduled to be completed in approximately 12 months. The primary recruitment will occur in the first 10 months, and the last two months will allow for unexpected delays.
- Participants will undergo study procedures for 12 months (+ 3 months).
- Participants will be recruited from each of the 20 study sites. Once recruitment at
 a site is completed, the site will be randomized and participants will be informed
 of the arm allocation. Participants assigned to the CHW arm will then be offered
 four CHW in-person visits and four follow-up phone calls over 12 months. The
 expectation is that in-person visits will align with well-child checks/WIC
 appointments every 3 months, so two visits in the first six months and two visits
 in the second six months, although the schedule is flexible. Telephone follow-up
 calls will follow in-person visits at a time determined meaningful by the CHW and
 family. Participants assigned to the usual care arm will be offered a CHW visit
 after they complete the final data collection at 12 months.
- Screening will occur at the study sites during the recruitment phase. Initial screening will be conducted verbally. Caregivers who are interested in participating will have an enrollment data collection visit scheduled. The study staff (two RAs) will conduct this visit in the family's home, at the recruitment site, or at another mutually agreed upon location. First, consent will be obtained. Then the staff will obtain survey responses by verbally asking questions about demographics, brushing, general health, social support, access to care, and health behaviors. Child dental plaque measurements will be obtained: disclosing solution will be applied to the child's teeth and the teeth will be photographed. If the data collection is occurring in the home, families will be asked to demonstrate tooth brushing and the technique and equipment will be documented. Data will be collected again by RAs at 6 months and 12 months.

- After sufficient participants have been enrolled from a site, the site will undergo randomization procedures. If the site is randomized to CHW services, all participants enrolled at that site will be offered the CHW intervention.
- Outcomes will be collected via self-report, clinical assessment, and observation of behaviors and equipment. This is described in detail in Section 3.2. Plaque will be captured via photographs in the field which will then be scored by a calibrated clinician at UIC.

5 STUDY ENROLLMENT AND WITHDRAWAL

5.1 Subject Inclusion Criteria

To be eligible to participate in these study activities, the caregiver/child dyad must meet the following criteria:

Caregiver:

- Provide a signed and dated informed consent form
- Age 18 or older
- Be the primary caregiver of a child age 6-36 months old. The primary caregiver is defined for this study as the person (or one of the people) who is consistently responsible for the child's daily routines and who is a legal guardian.
- If a child lives in multiple households, the caregiver must live with the child at least 5 days of the week.
- The child must be an active patient/client in the clinic/center where recruited.
- Speak English or Spanish
- Willing to comply with all study procedures and be available for the duration of the study

Child:

- Age 6-36 months old
- An active patient/client in the clinic/center where recruited
- A minimum of two fully erupted central maxillary incisors

5.2 Subject Exclusion Criteria

A caregiver/child dyad who meets any of the following criteria will be excluded from participation in this study:

- Child with medical condition that limits his or her ability to conduct the study activities (such as severe developmental or cognitive delay, ventilator or oxygen dependence, oral aversion, severe facial deformities)
- Anything that would place the individual at increased risk or preclude the individual's full compliance with or completion of the study
- Anything that would place the research or intervention staff at increased risk

5.3 Strategies for Recruitment and Retention

This trial will recruit a total of 420 caregiver/child dyads, 18-23 dyads from each of the 20 sites. In the CO-OP Chicago Pilot, 123 caregivers were approached, 58 agreed to participate, and 20 completed the enrollment. This suggests a screening to enrollment ratio of 6:1. Patient/client volumes vary by site, but the 20 sites together comprise at least 2400 potentially eligible subjects. Similar to the pilot, the RAs will approach

caregivers of young children who seem to be under the age of 3 in the waiting area of the clinic/center. The RA will assess the caregiver interest in the study and review inclusion/exclusion criteria. If the caregiver expresses a willingness and interest in study procedures, the RA will obtain caregiver's contact information and schedule an enrollment appointment. It took RAs about 3 hours of screening time for each enrolled family in the pilot. Families are given small incentives like toothbrushes for completing the screening.

Consent procedures will be conducted at the beginning of the enrollment visit, and the visit should last no more than 60 minutes. At the completion of the visit, participants will be offered \$40 and a flyer describing basic oral health tips (https://www.nidcr.nih.gov/ oralhealth/Topics/ToothDecay/Documents/healthy-mouth-for-your-baby-factsheet.pdf.)

Once enrolled, participants will be contacted again by RAs at 6 months and 12 months for data collection. Payment will be the same at those visits (\$40). In total, families that complete all data collections will receive \$120.

The contact procedures are detailed in Appendix D. Retention for all participants will be achieved by:

- Careful vetting of all research materials through a community advisory board to ensure participants feel connected to the trial;
- Using field staff who are engaging, respectful, and non-threatening;
- Collecting multiple types of contact information for participants including primary phone, back up phone, emails, address, back up address, and an alternative contact person's phone and address. RAs will clarify at each contact timepoint how participants prefer to be contacted (text, email, phone call) and when are the best times to reach them;
- Remuneration for data collection;
- Maintaining strong partnerships with the participant's clinic/WIC center.

Participants might experience a delay between enrollment and randomization while waiting for site to reach sufficient enrollment numbers. While waiting for randomization, research staff will call the family to verify contact information and reassure them about the study every 4 weeks.

5.4 Treatment Assignment Procedures

Participant treatment assignments are determined by their site of enrollment. Sites will be cluster randomized to CHW or usual care. This process is described in Section 5.4.1.

5.4.1 Randomization Procedures

Clinic and WIC sites will be randomized on the site level once enrollment has reached approximately 90% of goal (18-23 families) at each site. Simple cluster randomization with relatively small numbers of clusters is susceptible to baseline imbalance with

respect to cluster and participant characteristics between the intervention and comparison conditions. Thus, restricted randomization of clusters is commonly employed to enforce greater balance, which both eliminates potential bias and enhances power. We are using terminology from the review paper by Noah Ivers et al. where minimization and covariate-constrained randomization are special cases of a more general category of restricted randomization.³⁷ We will employ a stratified by clinic/WIC minimization method to ensure baseline characteristic balance at both cluster and participant level. Randomizing sites after approximately 90% of the enrollment goal will ensure blinding of RAs, site staff, and participants until most participants from each site are enrolled. (The last 10% of participants are often the slowest to recruit and this small number should not influence the participant-level covariate balance.) Cluster-level summary statistics regarding race and ethnicity characteristics of the site population (African American, Latino, or mixed) and site size (high, medium, low) will be used as cluster-level covariates for minimization. Clusterlevel randomization will be done by the UCSF Coordinating Center (CC). Once a site is randomized, the CC will inform the UIC project manager who will inform the site leadership of the site assignment via email and/or phone call. The UIC project manager will assign a CHW if randomized to that arm. The project manager will then inform the CHW of his/her participants and provide access to their contact information. UIC will send letters via mail to participants informing them of their site's assignment, and their CHW's information if applicable.

5.4.2 Masking Procedures

Although double blinding in a behavioral randomized clinical trial is not feasible, blinding will be maximized by utilizing independent outcomes assessors (research assistants) who will be blinded to study arm, and by reminding staff and partners about equipoise. Participants will be reminded at every contact to not disclose their study arm or any intervention they are or are not receiving. Investigators who supervise the CHWs and the project manager will be unblinded to treatment arm because they will need to work with the CHWs and monitor intervention fidelity and data accuracy. The USCF CC will also be unblinded to treatment arm. Study staff and investigators will not have access to interim outcomes data. Unmasking procedures are described in more detail in the Manual of Procedures.

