2.3.1 Potential Risks

Caregivers and children who participate in this study may experience discomfort with responding to questions, having their home and brushing observed, and having their children's teeth examined. They may not be comfortable with research staff or CHWs in their home. Staff will assure families that individual responses to study questionnaires

and individual oral exam and behavioral observation data collected for the study will not be shared with social service agencies, organizations, and people outside the study.

There is a risk of loss of confidentiality for all study participants. Precautions will be in place to minimize this risk, such as collecting only minimal identifying information and storing data collection documents in locked cabinets (located in locked offices), using unique study codes for participants, using encrypted computers, and maintaining electronic data files on a password-protected computer drive. Individual identifier numbers that are linked to participant contact information will be stored separately from the data. Compliance with all IRB regulations concerning data collection, data analysis, data storage, and data destruction will be strictly observed.

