7.2 Enrollment/Baseline Visit with RA (Visit 1, prior to Randomization)

- Obtain and document consent from subject on study consent form.
- Verify inclusion/exclusion criteria.
- Obtain self-reported data via verbal questionnaire. This includes demographic information, oral health behaviors, oral health risk factors, medical history questions, and family psychosocial functioning.
- Weigh child.
- Apply disclosing solution to child's teeth and obtain photographs for plaque assessment.
- If conducted in home, observe child brushing teeth and brushing equipment.
- Explain to family the randomization process and when intervention will start (Intervention will begin after randomization for families in sites that are randomized to receive CHW services. For families in sites that are randomized to not receive CHW services, they will be offered CHW services after study completion in one year.)
- Verify contact information.
- Thank family. Offer remuneration and give flyer on basic oral health recommendations.

7.3 Randomization, Day 0

Each site will be randomized to CHWs or usual care once recruitment is completed or near completion. See Section 5.4.1. for details.

7.4 Intervention in-person visits for CHW-sites only, start Day 1 and complete by Day 365

Four in-person visits will be offered to families. See Appendix D for details. The first two visits will be delivered between days 1-179. The third and fourth visits will be delivered between days 180-364.

7.5 Intervention telephone follow-ups for CHW-sites only, start Day 2 and complete by Day 365

Four follow-up telephone calls will be offered to families. The plan is for follow-up telephone calls to follow in-person visits.

7.6 6-Month Visit with RA, Day 180 (- 14 days, + 60 days)

- Obtain self-reported data via verbal questionnaire. This includes demographic information, oral health behaviors, oral health risk factors, medical history questions, and family psychosocial functioning.
- Weigh child.
- Apply disclosing solution to child's teeth and obtain photographs for plaque assessment.
- If conducted in home, observe child brushing teeth and brushing equipment.
- Record adverse events as reported by subject or observed by investigator.
- Verify contact information.
- Thank family. Offer remuneration.

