7.7 Final Study Visit with RA, Day 365 (+ 90 days)

- Obtain self-reported data via verbal questionnaire. This includes demographic information, oral health behaviors, oral health risk factors, medical history questions, and family psychosocial functioning.
- Weigh child.
- Apply disclosing solution to child's teeth and obtain photographs for plaque assessment.
- If conducted in home, observe child brushing teeth and brushing equipment.

- Record adverse events as reported by subject or observed by investigator.
- Remind family that we will send families a copy of the study results at the end of the study. Results will also be posted on the study website and displayed at the clinic/WIC center. Remind families that if they are in the usual care arm, they will soon receive a phone call from a CHW offering them a visit. Remind them that we may contact them in the future for follow-up studies if they agreed to that at the time of consent. Verify contact information.
- Thank family. Offer remuneration.

7.8 Intervention in-person visits for usual care-sites only, start Day 1 after final day collection and complete end of study

Families that are in usual care sites will be offered one CHW visit after they complete the final data entry. This is a courtesy visit to assess family risks and refer them to existing resources. The window for completion of this visit will last as long as funding is available for the CHWs.

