9.2 Time Period and Frequency for Event Assessment and Follow-Up

Unanticipated problems will be recorded in the data collection system throughout the study.

The PI will record all events with start dates occurring any time after informed consent is obtained until 7 (for non-serious AEs) or 30 days (for SAEs) after the last day of study participation. At each study visit, the investigator will inquire about the occurrence of AE/SAEs since the last visit. Events will be followed for outcome information until resolution or stabilization.

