Participated: 1 A	lot $_2\Box$ A little $_3\Box$ Not at all F	Person 4: First name	:
Relationship to child: _	F	Participated: $_1\Box$ A lot	$_2\Box$ A little $_3\Box$
Not at all Person 5: First name:	Relationship to child:		Participated:
1 □ A lot 2 □ A little 3 □ Not at all Person 6 : First	st name:	Relationship to o	child:

Based on NIDCR Clinical Trial (Interventional) Protocol Template v4.0 - 20140103

COordinated Oral Health Promotion (CO-OP) Chicago Trial Protocol

Version 2.0 19 March 2018

		Participated: ₁□ A lot	2□ A little	₃□ Not at all Person 7: First name:		
		Relationship to child:		Participated: 1 A lot	2□ A little	3
Not at all P	Person 8: Firs	t name:	Relation	ship to child:	Partio	cipated:
1□ A lot	2□ A little	₃□ Not at all				

SELF EVALUATION

Self-Ev	Self-Evaluation – How did I (the CHW) do today?			Н	ow much p	rogress do I feel	l was made on thi	s visit?		
1	2	3	4	5	-	1	2	3	4	-
Poor	Mediocre	Satisfactory	Good	Excellent		None	Some	Good	Great	

List anything else that happened or seems important here:

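### The masking reminder makes no exception for adverse events, yet the only scheduled post-randomization adverse-event assessments are at visits run by masked research assistants

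*Combined protocol and SAP*

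**What the plan says.** **Masking.** Section 5.4.2 relies on "independent outcomes assessors (research assistants) who will be blinded to study arm" and adds: "Participants will be reminded at every contact to not disclose their study arm or any intervention they are or are not receiving". The reminder does not mention adverse events, complaints or injuries. Unmasking procedures are left to the Manual of Procedures.

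**Who asks about adverse events.** Sections 7.6 and 7.7, whose headings both describe a visit with the RA, carry the instruction "Record adverse events as reported by subject or observed by investigator". Section 9.2 says: "At each study visit, the investigator will inquire about the occurrence of AE/SAEs since the last visit". It also has the PI record all events, and unanticipated problems recorded for the whole of the study.

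**When.** The AE row of Appendix A is marked at baseline, 6 months and final data collection. It is blank at Intervention Visits 1 to 4.

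**CHW contacts.** The visit and telephone scripts in Appendix G contain no AE question. The encounter form in Appendix H has no AE item. Its nearest field is the closing free-text line: "List anything else that happened or seems important here".

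**Foreseen risk.** Section 2.3.1 says of participating families: "They may not be comfortable with research staff or CHWs in their home".

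**The concern.** A family with a problem arising from a CHW visit is asked about adverse events by someone to whom it has been told not to mention the CHW. The protocol does not say which instruction gives way. Two things are at stake.

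- **Ascertainment.** Section 9.1 focuses safety monitoring on unanticipated problems. Under Section 9.1.1 these must be at least possibly related to taking part. Section 9.3.1 judges relatedness partly on timing relative to the intervention and on whether the event abates when the intervention stops. A family that follows the reminder strictly cannot give the RA those facts.
- **Masking.** A family that does explain the problem reveals its arm to the person who collects caregiver-reported brushing frequency, one of the two primary outcomes.

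Only the CHW arm receives the intervention during the trial, so intervention-related problems can be missed in that arm alone.

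**Working it through.** No power, rate or effect-size calculation applies. The check sets the sections side by side.

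1. **Scheduled AE assessments after randomization (Appendix A).** 6-month visit: 1. Final visit: 1. CHW Visits 1 to 4: 0. Total: 1 + 1 + 0 = 2, both at data-collection visits.

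2. **Who is present.** Sections 4, 7.6 and 7.7 have RAs conduct these visits, and Section 5.4.2 masks RAs. Section 9.2 names the investigator, but no investigator contact with families is scheduled. Either the RA asks, and the tension with Section 5.4.2 stands, or Section 9.2 describes an enquiry that nobody is scheduled to make. The text needs reconciling either way.

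3. **Order within the visit.** Sections 7.6 and 7.7 list the questionnaire (which holds the brushing question), then weight, plaque photographs and brushing observation, and only then AE recording. If the listed order is followed, a disclosure prompted by the AE question comes after that visit's outcomes are recorded. The order is not stated to be binding.

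4. **Which primary outcome is exposed.** Plaque is scored from photographs by a calibrated clinician (Section 4), not by the RA who hears the report. Brushing frequency is asked face to face by the RA. The main route to bias is therefore an RA unmasked at 6 months who asks the brushing question at 12 months. The documents do not say whether RAs return to the same families or sites.

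5. **Reach of one disclosure.** Assignment is by site (Section 5.4), with 18 to 23 families per site and 20 sites. One family's remark can reveal the arm of its whole site, which is 1/20 = 5% of the clusters. The number of interviews actually affected depends on how many of those families the same RA sees afterwards.

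6. **Other routes for a report.**
   - CHWs document problems after each encounter, and the supervisor and investigators review these records monthly (Section 6.3.3).
   - CHWs meet their supervisor weekly (Section 6.3.2).
   - The supervisor joins each CHW's first three home visits (Section 6.3.1) and at least one visit in 30 (Section 6.3.3).
   - The fidelity form scores whether the CHW asked for feedback (Appendix I).

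   None of these is a structured AE question put to the family. The notes, feedback and weekly meetings depend on the CHW, who may be the subject of the complaint. The reporting clocks in Section 9.4.1 start only when the investigator becomes aware.

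**The case against.** The strongest reply is that this is a gap in wording, already covered by the design.

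- **The reminder protects assessors and does not silence families.** It sits in the masking section, and an event can be described to an RA without naming the CHW. This stands. A reader might infer that families must either stay silent or break the rule, so that harms are suppressed. The documents do not support that; they support a risk of under-reporting.
- **The RA would be unmasked just as brushing is recorded.** A reader might infer this too, but the listed order in Sections 7.6 and 7.7 points the other way, and plaque is scored elsewhere. What remains is carry-over to a later interview.
- **Unmasked channels exist.** They do, and they reduce the concern. They are unstructured and mostly pass through the CHW, so they do not remove it.
- **Some material cannot be seen.** The Manual of Procedures is not among the documents, and the consent form (Appendix J) was removed from the copy reviewed. Either may give families a reporting route. The point is therefore limited to what the protocol body and its visible appendices say.
- **The foreseen harm is mild.** Discomfort with a visitor is not clearly a medical occurrence under Section 9.1.2, and because it is foreseen it may not count as unexpected under Section 9.1.1. This is fair. It means that not every complaint belongs under the Section 9.4.1 timelines.
- **The CHW arm could report more, because it has more staff contacts.** This is possible for total events. It is a reason to keep CHW-reported events out of the comparison between arms.

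Counting CHW contacts, or days between RA visits, would not measure under-reporting, because each enquiry covers the whole period since the last visit.

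**Conclusion.** The point holds as a risk that should be fixed. CHW-related problems may be under-reported in the CHW arm, or reporting one may unmask an RA, because a reminder without an AE exception meets an AE schedule confined to masked visits. Section 9.2 conflicts with the visit descriptions on who asks.

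The size can be stated only structurally: two scheduled post-randomization assessments, none at the four CHW visits, and 18 to 23 families whose arm one remark can reveal. The number of missed events cannot be estimated, because the documents give no harm rate.

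The masking consequence assumes that an RA unmasked at 6 months may conduct 12-month interviews at the same site. If RAs are rotated so that this cannot happen, that part largely falls away and the under-reporting risk remains. If the Manual of Procedures or the consent form already gives an unmasked reporting route, the main need is to say so in Sections 5.4.2 and 9.2.

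**What to change.** 1. **Section 5.4.2 and the assignment letter in Section 5.4.1.** Add an exception to the reminder, for example: *except to report a problem, injury or complaint, which you may raise at any time with the named study contact*. The contact should be an unblinded investigator who is not the CHW's direct supervisor. The project manager does not meet that condition, because Section 6.3.2 makes the project manager the CHW supervisor. Print the contact in the letter.

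2. **Sections 7.6, 7.7 and 9.2.** State who asks the AE question and make the three sections agree. If it is the RA, make the listed order binding: the AE question comes last, is worded the same for both arms, and any CHW-related report is passed to the named investigator without probing.

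3. **Appendix H.** Add one AE or complaint item that goes promptly to an investigator instead of waiting for the monthly review. The Section 9.4.1 timelines apply only if the event meets the unanticipated-problem criteria.

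4. **Reporting.** Compare arms only on events collected at RA visits. List CHW-reported events separately, because only one arm has CHW contacts during the trial.

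The cost is wording in the reminder script, one letter and one form, plus a short amendment to Section 9.2. No visits or staff are added. The downside is small: some families may reveal their arm, but with the AE question last this would come after that visit's outcomes are recorded.
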